Vital Signs		X	X	X	X	X	X	X		Perform prior to administering abemaciclib. Collect temperature, blood pressure, pulse oximetry, and pulse rate. Repeat if clinically indicated. Does not need to be repeated on Cycle 1 Day 1 if assessed at baseline $\le 3$ days prior to abemaciclib initiation.
ECOG Performance Status		X	X		X		X	X		Does not need to be repeated on Cycle 1 Day 1 if assessed at baseline $\le 3$ days prior to abemaciclib initiation.
Other Clinical Assessments										
12-Lead ECG	X						X			Single ECG performed locally. Participants must be supine for approximately 5 to 10 minutes before ECG collection and remain supine but awake during ECG collection. Repeat if clinically indicated.
AE Assessment	X				X		X	X		Collect continuously at every visit and throughout the study using CTCAE Version 5.0. See Section 8.3 for further details on AE and SAE reporting.

Screening, On-Treatment and Post-Treatment Schedule of Activities										
Study phases	Screening		On Treatment Cycle duration = 28 days				Post-Treatment Follow-up		Instructions	
	Baseline		Cycle 1		Cycle 2		Cycle 3 and subsequent	Short-Term Follow-Up a	Long-Term Follow-Up b	Procedures and disease assessments (tumor imaging) should be performed as per the schedule of activities, according to the calendar days, regardless of treatment delays.
Relative Day within Dosing Cycle & Visit Window ( $\pm n$ days)	$\le 28$	$\le 14$	D1 ( $\pm 3$ )	D15 ( $\pm 3$ )	D1 ( $\pm 3$ )	D15 ( $\pm 3$ )	D1 ( $\pm 3$ )	V801 (30 days $\pm 7$ )	V802-8XX (90 days $\pm 14$ )	
Laboratory Assessments										
Hematology		X	X	X	X	X	X	X		See Section 10.2, Appendix 2. Does not need to be repeated on Cycle 1 Day 1 if assessed at baseline $\le 3$ days prior to abemaciclib initiation. Repeat if clinically indicated.
Chemistry		X	X	X	X	X	X	X		See Section 10.2, Appendix 2. Does not need to be repeated on Cycle 1 Day 1 if assessed at baseline $\le 3$ days prior to abemaciclib initiation. Repeat if clinically indicated. Refer to Sections 8.2.2.1 and 10.5, Appendix 5, for hepatic monitoring.
PSA		X	X		X		X	X		See Section 10.2, Appendix 2.
Testosterone		X	X		X		X	X		See Section 10.2, Appendix 2.

Screening, On-Treatment and Post-Treatment Schedule of Activities										
Study phases	Screening		On Treatment Cycle duration = 28 days				Post-Treatment Follow-up		Instructions	

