	Baseline		Cycle 1		Cycle 2		Cycle 3 and subsequent	Short-Term Follow-Up a	Long-Term Follow-Up b	Procedures and disease assessments (tumor imaging) should be performed as per the schedule of activities, according to the calendar days, regardless of treatment delays.
Relative Day within Dosing Cycle & Visit Window ( $\pm n$ days)	$\le 28$	$\le 14$	D1 ( $\pm 3$ )	D15 ( $\pm 3$ )	D1 ( $\pm 3$ )	D15 ( $\pm 3$ )	D1 ( $\pm 3$ )	V801 (30 days $\pm 7$ )	V802-8XX (90 days $\pm 14$ )	
Tumor Assessment										
CT or MRI Scan of Chest, Abdomen, and Pelvis	X	Every 8 weeks, independent of treatment delays, (Day 1 of Cycle 3, 5, 7, 9, 11, etc...)					X	X	
Perform within 7 days prior to scheduled calendar day (except in screening period).
 
Unscheduled assessments if signs of disease progression are observed.
 
Perform within 14 days of symptomatic progression (if no radiographic progression yet) and prior to the start of new anticancer therapy, palliative radiotherapy or surgery.
	
Radionuclide Bone Scan	X	Every 8 weeks, independent of treatment delays, (Day 1 of Cycle 3, 5, 7, 9, 11, etc...)					X	X	
Patients discontinuing abemaciclib prior to documented radiographic progression will continue to have scheduled disease assessments until documented radiographic progression, start of new anticancer therapy, withdrawal of consent, death, or study completion, whichever occurs first.
	

Screening, On-Treatment and Post-Treatment Schedule of Activities										
Study phases	Screening		On Treatment Cycle duration = 28 days				Post-Treatment Follow-up		Instructions	
	Baseline		Cycle 1		Cycle 2		Cycle 3 and subsequent	Short-Term Follow-Up a	Long-Term Follow-Up b	Procedures and disease assessments (tumor imaging) should be performed as per the schedule of activities, according to the calendar days, regardless of treatment delays.
Relative Day within Dosing Cycle & Visit Window ( $\pm n$ days)	$\le 28$	$\le 14$	D1 ( $\pm 3$ )	D15 ( $\pm 3$ )	D1 ( $\pm 3$ )	D15 ( $\pm 3$ )	D1 ( $\pm 3$ )	V801 (30 days $\pm 7$ )	V802-8XX (90 days $\pm 14$ )	
MRI (preferred) or CT Scan of Brain	X									Only required at screening for patients with suspicion and/or symptoms of CNS involvement to rule out CNS metastases. Unscheduled assessments if signs of CNS disease progression are observed.

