Abbreviations: AE = adverse event; CNS = central nervous system; CT = computed tomography; CTC = circulating tumor cells; CTCAE = Common Terminology Criteria for Adverse Events (NCI 2017); D = day; ECG = electrocardiogram; ECOG = Eastern Cooperative Oncology Group (Oken et al. 1982); EORTC-QLQ-C30 = European Organization for the Research and Treatment of Cancer Quality of Life Questionnaire; FACT-GP5 = Functional Assessment of Cancer Therapy- General; MRI = magnetic resonance imaging; n = number; NRS = numeric rating scale; PD = pharmacodynamics; PGx = pharmacogenomics; PK = pharmacokinetics; PRO = patient-reported outcome; PRO-CTCAE = Patient-reported outcome Common Terminology Criteria for Adverse Events; PSA = prostate specific antigen; QoL = quality of life; SAE = serious adverse event; V = visit.

a Short-term follow-up begins when the participant and investigator agree that the participant will no longer continue study treatment and lasts approximately 30 days ( $\pm 7$  days).

b Long-term follow-up begins when the short-term follow-up period is completed and continues until the participant's death, loss to follow-up, or study withdrawal.

In all cases, no follow-up procedures will be performed for a participant who withdraws informed consent unless he has explicitly provided permission and consent.

Mobile healthcare service may be leveraged to collect and process lab samples in conjunction with a patient's visit, when deemed appropriate by the investigator and allowed by local laws and regulations.

Continued Access Schedule of Activities			
Study phase	Continued Access Treatment	Follow-up a	Instructions
	V501-V5XX	V901	
Procedure			
Abemaciclib	X		Orally twice daily on Days 1 through 28 of a 28-day cycle.
AE collection	X	X	
Assessments to be conducted at a minimum with each collection and dispensing study drug (every 28 days) from Visits 501-5XX. After V801, only SAEs that are related to study intervention or protocol procedure will be collected.
 
Frequency of evaluation, including efficacy assessments, is left to the judgement of the investigator based on standard of care.

Abbreviation: AE = adverse event; SAE = serious adverse event; V = visit.

a Continued access follow-up begins when the patient and the investigator agree that the patient will no longer continue abemaciclib in the continued access period and lasts approximately 30 days.

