## 7. Discontinuation of Study Intervention and Participant Discontinuation/Withdrawal

### 7.1. Discontinuation of Study Intervention

Participants may discontinue the study intervention at any time for any reason. Investigators should try to find out the reason and document it on the corresponding CRF.

The reason and date of discontinuation will be collected for all participants.

Participants with PSA-only progression should continue study intervention until disease progression (radiographic and/or symptomatic progression), when participant safety is not compromised.

Study intervention should be continued for as long as the participant consents and complies with study procedures and requirements, is tolerating the study intervention, until radiographic progression according to RECIST 1.1 for soft tissue and/or PCWG3 for bone; and/or until symptomatic progression.

Symptomatic progression is defined as:

- Symptomatic Skeletal Event (SSE), defined as symptomatic fracture, surgery or radiation to bone, or spinal cord compression
- Pain progression or worsening of disease-related symptoms requiring initiation of a new systemic anti-cancer therapy.
- Development of clinically significant symptoms due to loco-regional tumor progression requiring surgical intervention or radiation therapy.

When study intervention is discontinued due to symptomatic progression, the investigator should obtain CT/MRI and bone scan imaging within 14 days to assess for radiographic progression, prior to the participant initiating radiotherapy, surgery or subsequent anti-cancer therapy (whichever comes first).

Patients discontinuing study intervention due to documented radiographic progression will be followed for the development of symptomatic progression until start of new anticancer therapy, withdrawal of consent, death, or study completion, whichever occurs first.

Participants discontinuing study intervention prior to documented radiographic progression will continue to have scheduled disease assessments until documented radiographic progression, start of new anticancer therapy, withdrawal of consent, death, or study completion, whichever occurs first.

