**Disease Control Rate** is defined as the proportion of patients who have a soft tissue best overall response of CR, PR, or stable disease (SD) per RECIST 1.1, and do not have concurrent bone disease progression per PCWG3.

**Time to PSA progression** is defined as the time from the date of treatment initiation to the date of first observation of PSA progression. The PSA progression is defined as a  $\geq 25\%$  increase and an absolute increase of  $\geq 2$  ng/mL above the nadir (or baseline value if baseline is the smallest on study), which is confirmed by a second value obtained 3 or more weeks later. Any post-baseline PSA measurements within 12 weeks since baseline will be ignored in determining PSA progression (Scher et al. 2016).

**Time to Symptomatic Progression** is defined as the time from the date of treatment initiation to any of the following (whichever occurs earlier):

- Symptomatic Skeletal Event (SSE), defined as symptomatic pathological fracture, tumor-related orthopedic surgery, or external beam radiation to bone progression, or spinal cord compression.
- Pain progression or worsening of disease-related symptoms requiring initiation of a new systemic anti-cancer therapy.

- Development of clinically significant symptoms due to loco-regional tumor progression requiring surgical intervention or radiation therapy.

**Prostate Specific Antigen Response Rate** is defined as the proportion of participants with a reduction in PSA level of  $\geq 50\%$  from baseline (see Section 9.4.1), confirmed with a second assessment conducted at least 3 weeks later.

**PSA Change from Baseline to 13 Weeks** is defined as the individual proportion of rise or fall in PSA at 13 weeks relative to baseline (see Section 9.4.4). Missing observations will not be imputed.

**Maximum Decline in PSA** is defined as the relative change in PSA from baseline (see Section 9.4.1) to the lowest on-study value, occurring at any time point.

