6.7.2.5. Time to Prostate-Specific Antigen Progression

Prostate-specific antigen progression is defined as a $\geq 25\%$ increase and an absolute increase of ≥ 2 ng/mL above the nadir (or baseline value if baseline is the smallest on study), which is confirmed by a second value obtained 3 or more weeks later. Any postbaseline PSA measurements within 12 weeks since baseline will be ignored in determining PSA progression. Time to PSA progression is measured from the date of first dose to the date of first observation of PSA progression. Patients who have not had PSA progression will be censored at the day of their last PSA assessment (if available) or date of first dose if no postinitiation (ie, postbaseline) PSA assessment is available. The detailed censoring rules are described in [Table JPCY.6.2](#).

Time to PSA progression will be summarized and listed for all treated patients. The KM method (Kaplan and Meier 1958) will be used to estimate the time to PSA progression curve as well as landmark survival rates at 3, 6, 9, and 12 months.

Table JPCY.6.2. Time to PSA Progression Event/Censoring Scheme

Situation	Event/Censor	Date of Event or Censor
Confirmed PSA progression	Event	Date of first observation of PSA progression ^a
Not known to have had confirmed PSA progression confirmed	Censored	Date of last PSA assessment showing no evidence of PSA progression or date of first dose (whichever is later) ^b
Unless		
No baseline PSA assessment or no postbaseline PSA assessments available beyond 12 weeks since baseline	Censored	Date of first dose

Abbreviation: PSA = prostate-specific antigen.

- ^a To be specific, for confirmed PSA progression, the date of first observation of PSA progression is the date at which initial PSA progression is observed not the date that the PSA progression is later confirmed by a subsequent assessment.
- ^b To be specific, “last PSA assessment showing no evidence of PSA progression,” does not include the assessment showing initial/unconfirmed evidence of PSA progression.

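### On scheduled visits, a man who stops treatment at the Week 9 scan cannot have a confirmed PSA progression, so the Kaplan-Meier PSA-progression-free rates are likely overstated

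*SAP*

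**What the plan says.** **Event definition.** Protocol section 8.1.1 and SAP section 6.7.2.5 define PSA progression as a rise of at least 25% and at least 2 ng/mL above nadir, or above baseline if that is lowest, "which is confirmed by a second value obtained 3 or more weeks later". Early values do not count: "Any postbaseline PSA measurements within 12 weeks since baseline will be ignored in determining PSA progression".

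**Censoring.** Table JPCY.6.2 censors a man at the date of first dose if there is "No baseline PSA assessment or no postbaseline PSA assessments available beyond 12 weeks since baseline". Its note b says that an unconfirmed first rise cannot supply the censoring date, so the date moves back to an earlier value. The running text of the same section mentions first-dose censoring only when there is no post-baseline PSA at all. It points to the table for the detailed rules.

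**PSA collection.** The PSA row of Protocol section 1.3 has entries at screening, Day 1 of each cycle and V801. The long-term follow-up cell is empty. Footnote a places V801: "Short-term follow-up begins when the participant and investigator agree that the participant will no longer continue study treatment and lasts approximately 30 days" (±7 days).

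**Stopping.** Scans fall on Day 1 of Cycles 3, 5, 7 and so on, and may be done up to 7 days early. Under Protocol section 7.1, treatment continues while the participant consents, complies and "is tolerating the study intervention, until radiographic progression according to RECIST 1.1 for soft tissue and/or PCWG3 for bone" (or until symptomatic progression). Section 8.1.1 requires no confirmatory scan for soft-tissue progression.

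**Reporting.** The SAP gives a Kaplan-Meier curve for all treated patients, with rates at 3, 6, 9 and 12 months. The only sensitivity analysis in SAP section 6.7.3 is independent review of imaging.

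**The concern.** The endpoint looks for events only after 12 weeks and asks for two values, while PSA collection ends soon after treatment does. A man whose disease progresses on the first scan is off drug at about Week 9. His PSA may be rising steeply, but the schedule gives no opportunity to establish this under the definition.

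Kaplan-Meier estimation assumes that censored men have the same future risk as those still followed. Here the men censored first are those with the fastest radiographic progression. If PSA tends to progress in the same men, the curve describes mainly those who stayed on drug past Week 9, while being labelled as all treated patients. There is no control arm in which the same bias would appear, and no planned analysis would show it.

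**Working it through.** **The plan's own figures.** The plan states no figure for this endpoint. Its only sizing figures concern ORR, and they reproduce: with X binomial and n = 40, P(X ≥ 5) is 0.0480 at a true rate of 5% and 0.7367 at 15% (stated: 4.8% and 73.7%). They are not affected by this point.

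**Calendar check, in days from first dose.** Baseline is taken as day 0, because PSA is scheduled on Cycle 1 Day 1.
- Earliest qualifying first value: 12 × 7 = 84, so day 85.
- Earliest confirming value: 85 + 21 = day 106.
- Week 9 scan (Cycle 3 Day 1): nominal day 56. It can be as early as 56 − 7 = 49, and the visit as late as 56 + 3 = 59.
- V801 after a stop at that scan: nominal 56 + 30 = day 86; earliest 49 + 23 = day 72; latest 59 + 37 = day 96.
- If the stop decision comes as late as day 64, the latest V801 is 64 + 37 = day 101, still before day 106.
- If baseline were a screening value 14 days before first dose, the cut-off would be 84 − 14 = day 70. The Cycle 3 Day 1 PSA (day 59 at the latest) would still be excluded, leaving only V801.

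So at most one scheduled value qualifies, and a confirmed event cannot occur. With V801 on or before day 84, Table JPCY.6.2 censors the man at day 0. With V801 after day 84 and showing a first rise, he is censored at an earlier value. By contrast, a man who stops at Week 17 has PSA at days 112 and 112 + 30 = 142, which can confirm an event.

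**How many men (illustration).** Assume exponential rPFS and the SAP month of 365/12 = 30.42 days. The share progressing by day 56 is 1 − 2^(−(56/30.42)/median). The medians come from the two arms of an earlier-line trial cited in Protocol section 2.2.1.
- Median 3.7 months: 29.2%, × 40 = 11.7, about 12 men.
- Median 8.0 months: 14.7%, × 40 = 5.9, about 6 men.

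These are upper illustrations. rPFS includes deaths, and bone-only progressors stay on drug pending confirmation. If half of Week 9 progressors were bone-only, the 3.7-month share would be 29.2% × 0.5 = 14.6%.

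**Effect on the curve (simulation, 20,000 men per scenario).** Assumptions, none taken from the documents unless stated:
- Radiographic and PSA progression times are exponential and linked by a Gaussian copula.
- The PSA median is 3.7 months.
- Scans are every 56 days, PSA every 28 days plus V801, with Table JPCY.6.2 applied.
- The comparator samples PSA every 28 days after stopping.
- Death, new therapy and PSA measurement error are not modelled.

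| rPFS median (months) | Correlation | 6-month rate, as written | 6-month rate, PSA continued | Excess (points) |
|---|---|---|---|---|
| 3.7 | 0 | 37.1% | 35.6% | 1.5 |
| 3.7 | 0.3 | 42.7% | 35.7% | 7.0 |
| 3.7 | 0.6 | 48.8% | 35.5% | 13.3 |
| 8.0 | 0 | 36.3% | 34.8% | 1.5 |
| 8.0 | 0.3 | 38.8% | 35.1% | 3.7 |
| 8.0 | 0.6 | 42.0% | 36.0% | 6.0 |

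Men who stopped at the Week 9 scan contributed 0 events under the rule as written in every scenario. With median 3.7 months, correlation 0.6 and half of the Week 9 progressors kept on drug to Week 17, the excess falls to about 8 points.

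**The case against.** A reader might infer that nobody who progresses at Week 9 can ever be a PSA event. The documents do not support that. Under the bone rules in Protocol section 8.1.1, new bone lesions first seen at Week 9 need confirmation at least 6 weeks later or at Week 17. A bone-only progressor would normally still be on drug then, with PSA near days 112 and 142. Section 7.1 also allows treatment beyond progression in rare, approved cases, and an unscheduled later PSA could confirm a rise. The point therefore applies to men who stop at Week 9, on scheduled visits.

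A reader might also take the 13-point excess as established. It is not: it rests on a correlation of 0.6 that the documents do not give, and at zero correlation the excess nearly disappears. The comparator curve is also hypothetical, because some men will die or start other therapy.

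Finally, this is one of several secondary endpoints and is described without a test. Study success depends on ORR alone, and early radiographic failures are still counted in rPFS. All of this stands and limits the weight of the point. It does not remove the mechanism, which follows from the plan's own calendar, and no tested scenario gave a bias in the other direction.

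**Conclusion.** The point holds in limited form. On scheduled visits, a man who stops at the Week 9 scan has no route to a confirmed PSA event and leaves the risk set before he could have one. That part needs no modelling assumption.

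The upward bias is likely rather than proven. It requires radiographic and PSA progression to be positively associated, which is plausible but not quantified in the documents. With both medians at 3.7 months, the 6-month excess runs from 1 to 2 points (correlation 0) through 7 (0.3) to 13 (0.6), and is about 8 at 0.6 if half of Week 9 progressors are bone-only. The primary analysis is untouched. The SAP should address the point because, as planned, nothing in the report would show how many men were affected.

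**What to change.** Keep the confirmed definition and Table JPCY.6.2 as the main analysis. In SAP sections 6.7.2.5 and 6.7.3, pre-specify:

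1. A supplementary analysis in which radiographic progression or death before confirmed PSA progression counts either as an event (composite, Kaplan-Meier) or as a competing event (cumulative incidence of PSA progression). State which in advance.
2. Beside the main curve, the number of men who stopped too early to have a confirmable PSA event, including how many were censored at first dose.

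Counting a single raised V801 value as progression may be shown only as a worst-case bound, labelled as unconfirmed. It drops both the confirmation and the 12-week exclusion, and in simulation it overcorrects by about 2 to 7 points at zero correlation.

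The cost is a short SAP addition, one extra curve and one count, all from data already collected. The drawback is that the composite no longer measures PSA progression alone, so it should stand beside the main curve and not replace it.

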6.7.2.6. Prostate-Specific Antigen Response Rate

The PSA response rate is defined as the proportion of participants with a reduction in PSA level $\geq 50\%$ from baseline, confirmed with a second assessment conducted at least 3 weeks later. The PSA response rate will be listed and summarized for all treated patients.

6.7.2.7. Time to Symptomatic Progression

Time to symptomatic progression is defined as the time from first dose to any of the following (whichever occurs earlier):

- symptomatic skeletal event, defined as symptomatic fracture, surgery or radiation to bone, or spinal cord compression
- pain progression or worsening of disease-related symptoms requiring initiation of a new systemic anticancer therapy, and
- development of clinically significant symptoms due to locoregional tumor progression requiring surgical intervention or radiation therapy.

For patients not known to have had symptomatic progression at the time of data analysis, data will be censored on the last date at which no symptomatic progression is indicated.

Time to symptomatic progression will be summarized and listed for all treated patients. A KM analysis will be performed to estimate the time to symptomatic progression survival curve as well as quartiles and rates at 3-month intervals. As appropriate, these analyses will be repeated for each of the individual components of time to symptomatic progression.

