Symptomatic Progression			X		X		X	X	X	
Assess:
 
 
• Symptomatic skeletal event defined as symptomatic fracture, surgery, or radiation to bone or spinal cord compression
 
• Pain progression or worsening of disease-related symptoms requiring initiation of a new systemic anti-cancer therapy
 
• Development of clinically significant symptoms due to loco-regional tumor progression requiring surgical intervention or radiation therapy
 
 
Perform until evidence of symptomatic disease progression, start of new anticancer therapy, withdrawal of consent, death, or study completion, whichever occurs first.

Study Treatment										

Screening, On-Treatment and Post-Treatment Schedule of Activities										
Study phases	Screening		On Treatment Cycle duration = 28 days				Post-Treatment Follow-up		Instructions	
	Baseline		Cycle 1		Cycle 2		Cycle 3 and subsequent	Short-Term Follow-Up a	Long-Term Follow-Up b	Instructions
Relative Day within Dosing Cycle & Visit Window ( $\pm n$ days)	$\le 28$	$\le 14$	D1 ( $\pm 3$ )	D15 ( $\pm 3$ )	D1 ( $\pm 3$ )	D15 ( $\pm 3$ )	D1 ( $\pm 3$ )	V801 (30 days $\pm 7$ )	V802-8XX (90 days $\pm 14$ )	Procedures and disease assessments (tumor imaging) should be performed as per the schedule of activities, according to the calendar days, regardless of treatment delays.
Abemaciclib			Orally twice daily, on Days 1 through 28 of a 28-day cycle.						See Section 6.1	
Study Drug Compliance Assessment				X			X			
Review Patient Diary			X	X	X	X				Review patient diary at each study visit for completion of date and time for each dose taken on the day before PK sampling. After Cycle 3 Day 1, the diary is no longer required.
Post-study Treatment Collections										
Post-Discontinuation Anti-Cancer Therapies							X	X	Collect until death, withdrawal of consent, or study completion.	
Survival Status							X	X	Although preferable to collect during a clinic visit, if no procedures are required, survival information may be collected by contacting the patient or family directly (e.g., via telephone. This should be collected at minimum every 90 ( $\pm 14$ ) days if no other procedures are performed.	

Screening, On-Treatment and Post-Treatment Schedule of Activities									
Study phases	Screening		On Treatment Cycle duration = 28 days			Post-Treatment Follow-up		Instructions	

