## 6.6. Dose Modification

Dose adjustments (suspensions and reductions) will be made based on the clinical assessment of hematologic and nonhematologic toxicities (defined as an AE possibly related to abemaciclib per investigator judgment). The CTCAE v5.0 will be used to assess AEs. Abemaciclib may be suspended for a maximum of 28 days to allow a participant sufficient time for recovery from abemaciclib-related toxicity. If a patient does not recover from the toxicity within 28 days from the time of last treatment, the patient should be considered for permanent discontinuation from abemaciclib. In exceptional circumstances, a delay >28 days is permitted upon agreement between the investigator and the Lilly CRP/CRS.

Participants undergoing non-tumor related surgical procedures should follow the guidelines below:

- For minor surgeries and procedures (for example, ambulatory), investigators should treat as clinically indicated and closely monitor any signs of infection or healing complications.
- For major surgeries, the recommendation is to suspend dosing of abemaciclib for at least 7 days before surgery and may be resumed as clinically indicated.
- Consider monitoring neutrophils and platelets before surgery and before resuming abemaciclib. The scars should be aseptic and healing process be reasonable before resuming abemaciclib.

Dose reductions for abemaciclib should be performed as shown in the table below. Abemaciclib must be reduced sequentially by 1 dose level, unless an exception is granted in consultation with the Lilly CRP/CRS. For participants requiring a dose reduction of study intervention, any re-escalation to a prior dose level is permitted only after consultation with and approval by the Lilly CRP/CRS.

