#### **9.4.3. Secondary endpoint(s)**

Summaries of event rates, including radiologic ORR, and PSA-based response, will be defined as the proportion of all treated participants who achieve the specified response category.

Participants with a non-evaluable or unknown response per specified criteria will be considered non-responders for the purpose of calculating the response rate.

Detailed censoring rules for time to event (TTE) endpoints are described in the SAP. For all TTE endpoints, median event times and rates at various time points, with 95% CI, will be estimated using the Kaplan-Meier method (Kaplan and Meier 1958). Sensitivity analyses for TTE will be described in the SAP.

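### The SAP defines the symptomatic skeletal event more broadly than the protocol's efficacy definition, so time to symptomatic progression can count non-tumor fractures and bone operations

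*SAP*

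**What the plan says.** Time to symptomatic progression is a secondary efficacy endpoint with three components: a skeletal event, worsening pain or symptoms that lead to new systemic therapy, and locoregional symptoms that need surgery or radiation. The skeletal component is defined in four places.

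- Protocol 8.1.1 (efficacy definitions): "defined as symptomatic pathological fracture, tumor-related orthopedic surgery, or external beam radiation to bone progression, or spinal cord compression".
- SAP 6.7.2.7 (analysis): "symptomatic skeletal event, defined as symptomatic fracture, surgery or radiation to bone, or spinal cord compression".
- Protocol 7.1 (stopping treatment): "Symptomatic Skeletal Event (SSE), defined as symptomatic fracture, surgery or radiation to bone, or spinal cord compression".
- Protocol 1.3, Schedule of Activities: "Symptomatic skeletal event defined as symptomatic fracture, surgery, or radiation to bone or spinal cord compression".

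Death is not among the listed events. For patients without known symptomatic progression, SAP 6.7.2.7 states that "data will be censored on the last date at which no symptomatic progression is indicated". The planned output is a Kaplan-Meier curve, quartiles and 3-monthly rates, repeated by component where appropriate. This follows protocol 9.4.3: "For all TTE endpoints, median event times and rates at various time points, with 95% CI, will be estimated using the Kaplan-Meier method".

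**The concern.** The two texts that govern the endpoint cannot both be followed for a traumatic fracture or a bone operation unrelated to the cancer. Protocol 8.1.1 excludes it and the SAP wording includes it. Two programmers, one working from each document, could classify the same patient differently. The SAP does not present the difference as a deliberate change. What is at stake is which events count in a secondary efficacy endpoint, and so its curve and rates.

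A lesser matter concerns how the rates are read. With deaths censored, one minus the Kaplan-Meier estimate describes the risk as if no one died before symptomatic progression. In heavily pretreated metastatic disease some patients will die first, so this figure is not the share of patients who experience the event. No estimate that treats death as competing is planned.

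**Working it through.** **1. Definitions side by side.**

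| Element | Protocol 8.1.1 | SAP 6.7.2.7, protocol 7.1, Schedule of Activities |
|---|---|---|
| Fracture | symptomatic and pathological | symptomatic |
| Surgery | tumor-related, orthopedic | to bone, no cause required |
| Radiation | external beam, for bone progression | to bone |
| Cord compression | included | included |

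Every difference makes the SAP version the wider one.

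**2. Does the protocol elsewhere show which reading is meant?** Partly. Protocol 6.6 has separate rules for unrelated operations: "Participants undergoing non-tumor related surgical procedures should follow the guidelines below". For major surgery the advice is to "suspend dosing of abemaciclib for at least 7 days before surgery and may be resumed as clinically indicated". Non-tumor surgery is therefore not meant to end treatment, which favors the 8.1.1 reading for operations. No similar passage deals with a non-tumor fracture.

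**3. Size of the definition effect.** The documents give no count of affected events. One extra first event among 40 patients is 1/40 = 2.5 points as a crude proportion. As a Kaplan-Meier step it depends on the number at risk: with 20 at risk and a current estimate of 70% (an illustration), the step is 0.70/20 = 3.5 points.

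**4. The plan's own figures.** The documents state none for this endpoint. The primary rule (5 or more responders of 40) gives an exact binomial type I error of 0.0480 at a true rate of 5% and power of 0.7367 at 15%. These match the stated 4.8% and 73.7%. Nothing from symptomatic progression enters either calculation.

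**5. Kaplan-Meier against cumulative incidence.** The inputs are assumptions, because the documents give neither median:

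- median time to symptomatic progression absent death, m_s: 6, 12 or 24 months;
- median time to death without prior symptomatic progression, m_d: 11 or 30 months. The 11.0-month figure is all-cause median survival in the anti-androgen arm of the randomized cabazitaxel trial cited in protocol 4.2, an earlier-line population. Applying it in full to deaths before symptomatic progression is an upper-end choice.

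With constant, independent hazards h_s = ln 2/m_s and h_d = ln 2/m_d:

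- 1−KM = 1 − exp(−h_s t)
- CIF = h_s/(h_s + h_d) × [1 − exp(−(h_s + h_d) t)]

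Example with m_s = 6, m_d = 11, t = 6: h_s = 0.1155 and h_d = 0.0630. Then 1−KM = 50.0%, CIF = 0.647 × (1 − 0.343) = 42.5%, and the excess is 7.5 points.

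All results at 6 months (percent; excess in points):

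| m_s | 1−KM | CIF, m_d = 11 | Excess | CIF, m_d = 30 | Excess |
|---|---|---|---|---|---|
| 6 | 50.0 | 42.5 | 7.5 | 47.1 | 2.9 |
| 12 | 29.3 | 24.7 | 4.6 | 27.5 | 1.8 |
| 24 | 15.9 | 13.3 | 2.6 | 14.9 | 1.0 |

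For scale, the 95% half-width in 40 uncensored patients, 1.96 × √(p(1−p)/40), is 11.3 points at 15.9%, 14.1 at 29.3% and 15.5 at 50.0%. Every excess in the table is smaller.

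**6. Components, if analyzed.** The Schedule of Activities stops assessment at the first symptomatic progression, so the other components compete as well. For a component carrying one third of the hazard, h_c = h_s/3 and the competing hazard is 2h_s/3 + h_d. The 6-month excess is then 0.7 to 6.5 points over the same grid.

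**The case against.** **On the definition.** The event is headed symptomatic progression, and sites assess it as disease progression. An investigator might never record a traumatic fracture or elective joint operation under it, in which case nothing extra is counted. The short wording also stands in three of four places, so 8.1.1 could be the text that is out of line. The first argument is fair, and it is why the affected count may be zero. It does not remove the conflict, because the SAP wording contains no such limit and the CRF is not available to settle it. On the second, 8.1.1 is the section that defines the efficacy measures, and protocol 6.6 points the same way for surgery.

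**On Kaplan-Meier.** The SAP never calls its rates a proportion of patients. Kaplan-Meier with deaths censored is a valid net estimate under independent censoring. Protocol 9.4.3 prespecifies it for all time-to-event endpoints, and time to PSA progression follows the same convention. The censoring sentence already covers every patient without the event, including those who die or start new therapy; it simply does not name them. Component analyses are only to be done as appropriate. Listings and a death summary allow crude counts. All of this stands and reduces the competing-risk point to a suggestion.

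**Stronger readings a reader might infer.**

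- That the planned rates are wrong. They are not; they answer a different question from the share of patients affected.
- That the gap is large. At 12 months, with both medians set to 6 months, it is 28.1 points. But a 6-month median implies a hazard of death before symptomatic progression 11/6 ≈ 1.8 times the full 11.0-month survival hazard, and nothing in the documents supports that. With m_s = 12 and 25% or 50% of that survival hazard, the 12-month excess is 3.9 or 7.5 points.
- That the rates must overstate the share truly affected. The excess over estimated cumulative incidence is assured when deaths precede later events. However, long-term visits are 90 days apart, so progression shortly before death can be missed.
- That six months of follow-up is guaranteed. The primary analysis is timed only approximately, and SAP 6.7.1 allows it earlier.

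**Conclusion.** The definition conflict is a real but minor error. SAP 6.7.2.7 omits limits that protocol 8.1.1 sets on fractures, surgery and radiation, and the protocol repeats the short wording in 7.1 and the Schedule of Activities. Its effect cannot be sized from the documents and may be nil.

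The competing-risk point holds only as a supplement. One minus Kaplan-Meier lies above the cumulative incidence of symptomatic progression whenever patients die first. Under constant, independent hazards and the assumed medians (6 to 24 months for symptomatic progression, 11 to 30 for death without it), the excess at 6 months is about 1 to 7.5 points, inside the sampling error of a 40-patient study.

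The endpoint is descriptive and has no comparator. The primary ORR decision, its alpha and power, and the sample size do not change.

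**What to change.** 1. Copy the skeletal-event definition of protocol 8.1.1 into SAP 6.7.2.7 for the efficacy endpoint.
2. Check that the data collected identify whether a fracture or bone operation was tumor-related. This is a check, not a claimed gap.
3. Leave protocol 7.1 to the sponsor as a separate decision. It is a treatment-discontinuation rule, so narrowing it changes patient management and is more than a wording alignment.
4. As a supplement, report Aalen-Johansen cumulative incidence at the 3-monthly time points beside the planned Kaplan-Meier, with death competing. If component analyses are done, let the other components compete too. Give the number of patients censored at new anticancer therapy, because cumulative incidence still treats that censoring as independent.

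The cost is a few lines of SAP text and routine programming. Kaplan-Meier stays, so protocol 9.4.3 is unchanged. The downsides are two estimates for one secondary endpoint and possibly slightly fewer counted events.
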